5.7.1 RECIST version 1.1

RECIST is a set of published rules that define when cancer patients improve ("respond"), stay the same ("stabilize"), or worsen ("progression") during treatments. The original criteria were published in February 2000 by an international collaboration including the European Organization for Research and Treatment of Cancer (EORTC), National Cancer Institute (NCI) of the United States and the National Cancer Institute of Canada Clinical Trials Group. RECIST 1.1, published in January 2009, is an update to the original criteria and will be used for this study.

Refer to [Appendix A](#) for definition of target lesions, methods of measurement and all other related criteria for RECIST version 1.1. The following summarizes the definitions of the criteria used to determine objective tumor response for target lesions:

- **Complete Response (CR):** Disappearance of all target lesions. Any pathological lymph nodes (whether target or non-target) must have reduction in short axis to <10 mm.
- **Partial Response (PR):** At least a 30% decrease in the sum of diameters of target lesions, taking as reference the baseline sum diameters.
- **Progressive Disease (PD):** At least a 20% increase in the sum of diameters of target lesions, taking as reference the smallest sum on study (this includes the baseline sum if that is the smallest on study). In addition to the relative increase of 20%, the sum must also demonstrate an absolute increase of at least 5 mm. (Note: the appearance of one or more new lesions is also considered progression).
- **Stable Disease (SD):** Neither sufficient shrinkage to qualify for PR nor sufficient increase to qualify for PD, taking as reference the smallest sum diameters while on study.

5.8 Subject Discontinuation

Subjects will receive study treatment for up to four cycles (after the initial seroconversion dose) or until treatment discontinuation for one of the reasons listed below. However, subjects may discontinue study treatment or withdraw their consent to participate in the study at any time without prejudice. All reasons for discontinuation or withdrawal from trial will be recorded.

Reasons for subject discontinuation by the Investigator may include, but are not limited to, the following:

- Death
- Confirmed radiographic disease progression (Note: With approval of the Lead PI, a subject may be granted an exception to continue on study treatment with confirmed radiographic progression if clinically stable or clinically improved.)
- Significant noncompliance by subject or Investigator
- Investigator or Lead PI determination that it is no longer safe and/or no longer in the subject's best interest to continue participation
- Withdrawal of consent

- Lost to follow-up
- Necessity for treatment with other anticancer treatment prohibited by protocol
- Sexually active subjects who refuse to use medically accepted methods of contraception during the course of the study and for 3 months following the last dose of study drug
- Women who become pregnant or are breast feeding
- Request by regulatory agencies for termination of treatment of an individual subject or all subjects under the protocol

6.0 STUDY DRUGS

6.1 Treatment Compliance and Study Drug Accountability

The Investigator will maintain accurate records of receipt of study drug, including dates of receipt. In addition, accurate records will be kept regarding when and how much study drug is dispensed and used by each subject in the study. Reasons for deviation from the expected dispensing regimen must also be recorded. At completion of the study, to satisfy regulatory requirements regarding drug accountability, all unused study drug will be reconciled and destroyed in accordance with applicable state and federal regulations.

6.2 Talimogene Laherparepvec

Talimogene laherparepvec (T-VEC) is provided as a sterile frozen liquid in a single-use 2.0 mL cyclic olefin polymer plastic resin vial. Each vial will contain talimogene laherparepvec at a nominal concentration of 10^6 PFU/mL or 10^8 PFU/mL in an aqueous sodium phosphate buffer with sodium chloride, sorbitol, and myoinositol added as stabilizers and water for injection.. Each vial is intended for single use only.

Talimogene laherparepvec will be presented as a sterile, semi-translucent to opaque solution for injection (opacity is different for each concentration) preservative-free frozen liquid in a single use 2 mL cyclic olefin polymer (COP) plastic resin vial. Each vial will contain talimogene laherparepvec at a nominal concentration of 10^6 PFU/mL or 10^8 PFU/mL in an aqueous sodium phosphate buffer with sodium chloride, sorbitol and myo-inositol added as stabilizers and water for injection (WFI). Vials are appropriately filled to ensure that a sufficient deliverable dose is provided. Each 2 mL vial will contain approximately 1.15 mL of talimogene laherparepvec with a 1.0 mL deliverable volume. Each vial is intended for single use only.

The vial caps are color coded to easily distinguish between the 10^6 PFU/mL and 10^8 PFU/mL vial concentrations.

6.2.1 Storage and Handling

Talimogene laherparepvec should be stored protected from light and according to the storage and expiration information (where required) provided on the label that is affixed to the package containing the investigational product. Talimogene laherparepvec should be thawed per the instructions provided in the pharmacy manual. Vials should be checked for cracks or damage that may occur during the thawing process if not performed properly. Drug vials will be destroyed on site once Product complaint has been resolved. See Pharmacy Information Guide.**Special Instructions for Use and Handling**

Follow local institutional guidelines for handling and administration, personal protective equipment, accidental spills, and waste disposal.

- Wear protective gown or laboratory coat, safety glasses, or face shield and gloves while preparing or administering talimogene laherparepvec. Cover any exposed wounds before administering. Avoid contact with skin, eyes or mucous membranes.
- After placement of the IP catheter, there will be a gauze and occlusive dressing placed over the puncture site for 7 days. Replace dressing if it falls off during this time.
- Dispose of all materials that have come in contact with talimogene laherparepvec (e.g., vial, syringe, needle, any cotton or gauze) in accordance with local institutional procedures.
- In the event of an accidental occupational exposure to talimogene laherparepvec (e.g., through a splash to the eyes or mucous membranes) during preparation or administration, flush with clean water for at least 15 minutes. In the event of exposure to broken skin or needle stick, clean the affected area thoroughly with soap and water and/or disinfectant.
- Spills should be treated with a virucidal agent such as 1% sodium hypochlorite or Virkon®. All materials contaminated with talimogene laherparepvec must be disposed of in compliance with local institutional guidelines. Incineration is appropriate.
- Advise subjects to place used dressings and cleaning materials in a sealed plastic bag and dispose in household waste or return to study site depending on local guidance.

The use of a microbiological safety cabinet or hood for the dispensing of talimogene laherparepvec or for talimogene laherparepvec to be drawn up into syringes is not required for 1 mL stoppered vials. As such, it is appropriate to dispense vials of drug such that product is then drawn up into syringes in the room used for product administration, although this may also optionally occur elsewhere (e.g., in the pharmacy).

6.2.2 Administration

All eligible subjects will have a Bard peritoneal catheter placed prior to the initiation of therapy. Talimogene laherparepvec will be administered via intraperitoneal (IP) administration. The planned dose of talimogene laherparepvec (measured as plaque forming units or PFU) will be delivered in a 500 mL volume of normal saline. After the infusion, patient should roll to the right side, wait 10 minutes, then roll to the left side and wait an additional 10 minutes, and repeat this procedure of rolling to the right side and the left side every 10-15 minutes to ensure exposure of the virus to the peritoneal surfaces where disease is located. Patients will have vital signs (blood pressure, pulse, temperature, and respiratory rate) taken every 15 minutes for the first hour after infusion, then remain under observation for an additional hour to ensure no significant toxicity is endured as a result of the administration. At the end of the second hour, vitals should be taken again prior to discharge. This procedure should be repeated each of the 5 potential times that talimogene laherparepvec is administered throughout the course of the study.

6.3 Concomitant Medications/Vaccinations

Concomitant medications will be documented throughout the study. Medications or vaccinations specifically prohibited in the exclusion criteria are not allowed during the ongoing trial. If there is a clinical indication for one of these or other medications or vaccinations specifically prohibited during the trial, discontinuation from trial therapy or vaccination may be required. The Investigator should discuss any questions regarding this with the Lead PI.

6.3.1 Acceptable Concomitant Medications

All treatments that the Investigator considers necessary for a subject's welfare may be administered at the discretion of the Investigator in keeping with the local standards of medical care. All concomitant medication received from the date of signed informed consent through 30 days after the last dose of

study drug should be recorded on the CRF including all prescription, over-the-counter (OTC), herbal supplements, and IV medications.

Abstinence is acceptable if this is the usual lifestyle and preferred contraception for the subject. Otherwise, subjects of reproductive potential must agree to use two birth control methods after informed consent is signed through 90 days after the last dose of study drug. The two methods can either be two barrier methods or a barrier method plus a hormonal method to prevent pregnancy. The following are considered adequate barrier methods of contraception: diaphragm with spermicide (cannot be used in conjunction with cervical cap/spermicide), cervical cap with spermicide (nulliparous women only), contraceptive sponge (nulliparous women only), and male condom or female condom (cannot be used together). Appropriate hormonal contraceptives will include oral contraceptive pill (estrogen/progestin pill or progestin-only pill), contraceptive skin patch, vaginal contraceptive ring, or subcutaneous contraceptive injection.

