All patients will receive an initial seroconversion dose of intraperitoneal talimogene laherparepvec 4×10^6 PFU on Cycle 1 Day 1 to enable seroconversion as described in the currently approved treatment protocol for the treatment of cutaneous melanoma. Three weeks after the initial seroconversion dose, patients will receive talimogene laherparepvec at the dose level for the cohort for which they are enrolled every 2 weeks for up to 4 doses (in addition to the initial seroconversion dose, which all patients will receive). The length of the first cycle is 5 weeks and subsequent cycles are 2 weeks in duration.

In the Dose Escalation Cohort, three subjects will be enrolled at the starting dose of 4×10^6 PFU, and the dosing will continue in the standard '3+3' dose escalation scheme. If the starting dose is tolerated, enrollment will continue at 4×10^7 and 4×10^8 PFU. Once the MTD is determined, six subjects will be enrolled to the Dose Expansion Cohort at the MTD. All subjects will be dosed with talimogene laherparepvec IP once every 2 weeks for up to 4 doses (in addition to the initial seroconversion dose, which all patients will receive).

Study Assessments

Safety: Toxicity and safety assessments will be performed weekly during the 5 weeks, then every 2 weeks for up to 4 treatment visits. These assessments will include vital signs, ECOG performance status, medical history, physical examination, complete blood count (CBC), biochemistry, creatinine, AST, ALT, and bilirubin. Toxicities will be recorded using National Cancer Institute Common Terminology Criteria for Adverse Events (NCI-CTCAE) version 5.0. General symptom management and supportive care will be provided as clinically indicated to ensure optimal patient care. After discontinuation of study treatment, subjects will have toxicity and safety assessments 30 days after last dose of study drug.

Tumor Assessments

Restaging scans and blood tumor markers will be repeated at the end of cycle 4, after receipt of the fifth dose of study drug. Tumor response will be assessed using treating physician's discretion, based on a composite of RECIST 1.1 measurements, blood tumor markers (CEA or CA-125), measurements of abdominal girth, and/or clinical response.

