10. Requiring intermittent or chronic systemic (intravenous or oral) treatment with an antiherpetic drug (e.g., acyclovir), other than intermittent topical use.
11. Prior treatment with talimogene laherparepvec or any other oncolytic virus.

12. Subject has known sensitivity to talimogene laherparepvec or any of its components to be administered during dosing.
13. Prior therapy with tumor vaccine.
14. Receipt of a live vaccine within 28 days prior to enrollment.
15. Known to have acute or chronic active hepatitis B or C infection (active, previously treated, or both).
16. Known history of HIV infection.
17. Active infection or fever $\geq 101.3^{\circ}\text{F}$.within 3 days of port placement. .
18. Bleeding disorders that would preclude intraperitoneal port placement.
19. Refractory ascites that requires palliative paracentesis more frequently than once a month. Any other medical condition, including mental illness or substance abuse, deemed by the Investigator to be likely to interfere with a patient's ability to sign informed consent, cooperate and participate in the study or interferes with the interpretation of the results.
20. History of other malignancy within the past 5 years.
21. Female subjects who are pregnant or breast-feeding, or planning to become pregnant during study treatment or through 90 days after the last dose of talimogene laherparepvec.
22. Subjects of childbearing potential who are unwilling to use acceptable method(s) of effective contraception during study treatment and through 90 days after the last dose of talimogene laherparepvec.
23. Sexually active subjects and their partners unwilling to use male or female latex condom to avoid potential viral transmission during sexual contact while on treatment and within 90 days after treatment with talimogene laherparepvec.

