5.7 Tumor Assessments

Tumor Response will be assessed via a composite of a variety of endpoints and ultimately, the treating physician's judgment and assessment of these endpoints. Given the variability in clinical presentation of these malignancies, radiographic imaging findings, and baseline laboratory values, assessing tumor response may take into account clinical features, radiographic response, laboratory response, and clinical endpoints.

Clinical features may include, but are not limited to, performance status (ECOG or Karnofsky score), abdominal girth, development of bowel obstructions felt to be resulting from peritoneal tumor deposits, development of clinically-evident ascites, and frequency of paracenteses due to malignant ascites.

Radiographic response may be used to track those patients who have radiographically-evaluable tumor deposits at baseline, which may be prone to following with serial imaging. For a subset of these patients who have such radiographically-evaluable lesions, it may be possible to assess tumor response based on serial imaging (CT chest/abdomen/pelvis with and without contrast and/or MRI or PET imaging), using RECIST version 1.1 criteria. Some peritoneal surface malignancies will not be amenable to grading using RECIST version 1.1 criteria. However, there are other imaging scoring systems such as the SPAAT[11] Score or a modified peritoneal cancer index based upon multi-detector CT imaging [12] which may be helpful in establishing a radiographic determination of tumor response to therapy. The exact method of analyzing a given patient's imaging will depend on that patient's radiographic findings at baseline, and the radiologist's determination of the best method of following serial changes in imaging.

For those patients who have elevated blood tumor markers at baseline, following the response of these tumor markers to therapy will factor into assessing tumor response to therapy.

Clinical endpoints of progression-free survival and overall survival will also be used to assess response to therapy.

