Given the heterogeneity in presentations of patients with peritoneal surface malignancies, patients will likely be followed by a composite of a variety of the above endpoints, and these endpoints may be different from patient to patient. However, for a given patient, all attempts will be made to use the same method for tumor assessment at every assessment timepoint. Progressive disease (PD) may manifest in findings such as significant clinical progression, evidence of 20% increase in disease seen on

imaging, and/or increase in tumor marker by 20% over baseline. Response may manifest in findings such as improvement in clinical symptoms, evidence of 30% decrease in measurable tumor burden, and/or 30% decrease in tumor marker from baseline.

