6.3.2 Prohibited Concomitant Medications

Subjects are prohibited from receiving the following therapies during the Screening and Treatment Period of this study:

- Antineoplastic systemic chemotherapy or biological therapy
- Immunotherapy not specified in this protocol
- Chemotherapy not specified in this protocol
- Investigational agents other than talimogene laherparepvec
- Radiation therapy (Note: Radiation therapy to a symptomatic solitary lesion may be allowed with the approval of the Lead PI.)
- Live vaccines within 30 days prior to the first dose of study drug and while participating in the study. Examples of live vaccines include, but are not limited to, the following: measles, mumps, rubella, varicella/zoster, yellow fever, rabies, BCG, and typhoid vaccine.
- Systemic immunosuppressive therapy within 2 weeks including oral steroid doses > 10 mg/day of prednisone or equivalent within 7 days prior to enrollment.
- Antiherpetic drugs such as acyclovir. Intermittent topical use is permitted.

Subjects who, in the assessment by the Investigator, require the use of any of the aforementioned treatments for clinical management should be removed from the trial. Subjects may receive other medications that the Investigator deems to be medically necessary.

There are no prohibited therapies during the Follow-up Period.

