9.1.4 Exploratory Endpoints

In addition to defining the MTD, the study will provide useful preliminary data concerning efficacy. Methods of assessing response will be specific to each individual patient as described in Section 5.6. In the subset of patients with radiographically measurable disease RECIST 1.1 criteria will be used.

Patients in the per protocol population will be classified as responder or non-responder and the proportion of patients exhibiting response at trial closure by any criteria will be estimated by the 90% confidence interval. Patients who experience a radiographic/tumor marker CR will undergo confirmatory laparoscopy.

Time to progression measured from study entry to documented progression of disease will be estimated by the method of Kaplan-Meier in the intent-to-treat population. Patients who withdraw from the trial prior to disease progression, are either lost to follow-up, die or begin alternative treatments prior to progression, will be censored at the date considered to be lost to follow-up, date of death, or the first day of alternative therapy.

For all efficacy endpoints, analyses will be performed overall and in the patients treated at the MTD. These analyses are primarily exploratory since the data will be from only a limited number of patients available for the study.

As a first approach to addressing our exploratory aim of evaluating changes in peritoneal cavity leukocyte populations after the treatment of peritoneal surface dissemination of gastrointestinal, fallopian tube, ovarian, and primary peritoneal cancers with talimogene laherparepvec, we will perform multi-color flow cytometry analysis on peritoneal lavage fluid from patients at baseline (prior to seroconversion dose on C1D1), prior to treatment on C2D1, and on C4D1. If the subject comes off treatment mid cycle, there will be an additional plasma sample at the time of disease progression or off treatment. Immune cells will be stained with fluorescent antibodies specific for markers of major leukocyte subsets as commonly performed by the [name] Lab.

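### Response is counted on any criterion, with no rule for girth or symptom change after ascites drainage or (by narrow exception) radiotherapy, so supportive-care relief can enter the exploratory response rate

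*Combined protocol and SAP*

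**What the plan says.** **How response is judged.** Under Tumor Assessments, the synopsis leaves response to the treating physician, "based on a composite of RECIST 1.1 measurements, blood tumor markers (CEA or CA-125), measurements of abdominal girth, and/or clinical response". Section 5.7 names girth among the clinical features and adds: "Response may manifest in findings such as improvement in clinical symptoms". No threshold, duration or attribution rule is attached to symptom improvement. The same section lists, as features that may be considered, "development of clinically-evident ascites, and frequency of paracenteses due to malignant ascites".

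**How response is counted.** Section 9.1.4 says: "Methods of assessing response will be specific to each individual patient". Per-protocol patients are then classed as responder or non-responder, and the proportion responding on any criterion at trial closure is given with a 90% confidence interval. The only rule there for other treatment is censoring, and it applies to time to progression.

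**What care is available on study.** Section 6.3.1: "All treatments that the Investigator considers necessary for a subject's welfare may be administered at the discretion of the Investigator". Exclusion 19 in Section 4.2 bars "Refractory ascites that requires palliative paracentesis more frequently than once a month", so patients drained monthly or less often can enrol. Drainage is not on the prohibited list in 6.3.2. Radiotherapy is on that list, with a note: "Radiation therapy to a symptomatic solitary lesion may be allowed with the approval of the Lead PI". The section then says that subjects who require a listed treatment should be removed from the trial.

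**What is recorded.** The CRF instruction in 6.3.1 names medications of several kinds. It does not name drainage procedures or radiotherapy.

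**The concern.** Drainage reduces girth directly and relieves distension. Radiotherapy is given to relieve a symptom and may shrink the lesion. Both can therefore produce findings that the composite accepts as response when the virus has done nothing. If response on any criterion is enough and no rule addresses such findings, relief from supportive care can be reported as tumour response.

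The trial is small, open-label and single-arm, so no control group would show how much of the reported response has this source. The CRF instruction does not ask for drainage or radiotherapy, so the question could not reliably be settled afterwards either. What is at stake is the reading of the preliminary efficacy data that 9.1.4 says the study will provide.

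**Working it through.** **1. Can supportive-care relief be counted under the rules as written?**

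- *Is a clinical finding alone enough?* Yes. The synopsis joins the components with and/or, and 9.1.4 accepts any criterion. Symptom improvement is an explicit example of response in 5.7. Girth is a component in the synopsis and 5.7 but is not among the response examples in 5.7, so it is the weaker route.
- *Is drainage possible on study?* Yes. It falls under the general clause in 6.3.1, and it is foreseen by exclusion 19 and by the reference to paracentesis frequency in 5.7.
- *Is radiotherapy possible on study?* Only by exception in 6.3.2, and the removal sentence in the same section pulls the other way.
- *Does another rule remove such a case?* None was found. Non-evaluability for efficacy in 3.1 turns on missing the initial restaging. Confirmatory laparoscopy in 9.1.4 applies only to radiographic or marker complete responses. Appendix A says lesions in a previously irradiated area are usually not measurable and asks protocols to set the conditions; this protocol sets none, and a lesion irradiated during the study is not addressed.

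**2. Is girth measured in a way that limits the problem?** It is scheduled at screening, Day 1 of each cycle and the 30-day visit (5.1, 5.3, 5.4, Appendix C). Each dose puts 500 mL into the peritoneum (6.2.2), and no rule says whether girth is taken before or after the infusion, or how it is timed relative to drainage. The C4D14 restaging list in 5.3 contains scans and markers, not girth.

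**3. Size of one misattributed case.** The plan states no precision figure for response. Its nearest figure, in 9.1.3 for cytokine change at n = 12, is ±0.237. It reproduces as 1.645 × √(0.25/12) = 0.237, which confirms n = 12 as the planned MTD group. The synopsis gives 12 to 24 evaluable subjects overall. I take 12 and 24 as denominators; the per-protocol set could be smaller.

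One case adds 1/12 = 8.3 points or 1/24 = 4.2 points. The exact (Clopper-Pearson) 90% limits are the 0.05 quantile of Beta(x, n−x+1) and the 0.95 quantile of Beta(x+1, n−x). For x = 0 and n = 12 the upper limit is 1 − 0.05^(1/12) = 0.221.

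| Misattributed cases, no true responder | n = 12 | n = 24 |
|---|---|---|
| 0 | 0% (0 to 22.1%) | 0% (0 to 11.7%) |
| 1 | 8.3% (0.4 to 33.9%) | 4.2% (0.2 to 18.3%) |
| 2 | 16.7% (3.0 to 43.8%) | 8.3% (1.5 to 24.0%) |

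These figures hold for any misclassified subject, whatever the cause. The documents give no frequency of drainage, radiotherapy or misattribution, so the table is an illustration and not a forecast.

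**The case against.** The best defence is that 5.7 already directs the physician to ascites and paracentesis frequency, next to girth. A physician who weighs these would not credit a fall in girth to the drug just after drainage. That stands as a partial safeguard. It is partial because the list is permissive and says nothing about how the features combine.

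Three stronger readings are tempting, and the documents do not support them.

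- *A reader might infer that radiotherapy is freely allowed on treatment.* It is prohibited, subject to one exception that needs Lead PI approval, in a section that also says such subjects should be removed. Metastases outside the peritoneal surfaces are excluded (4.2, no. 5), so few subjects are likely to have a solitary symptomatic lesion.
- *A reader might infer that the bias can only favour the drug.* Girth taken after a 500 mL infusion would be larger, a baseline taken soon after drainage would make later girth look worse, and re-accumulating ascites can count against the patient. Overstatement is likely but not shown.
- *A reader might infer that every girth or symptom change after drainage should be discarded.* The only on-treatment restaging is at C4D14, so a rule reaching back to the previous tumour assessment would cover the whole treatment period. A patient who went from monthly drainage to a single drainage would lose credit for what may be real benefit.

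It is also fair that a short-lived fall after drainage may not last to trial closure, and that the protocol sets no girth threshold, so no particular change in centimetres can be called a misclassification.

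**Conclusion.** The gap is real and minor. As written, 9.1.4 can count relief from drainage, or more rarely from radiotherapy allowed by exception, as tumour response, and the specified records would not reveal it. The likely effect is to overstate the response proportion, by 8.3 points per case at n = 12 or 4.2 at n = 24. This rests on those denominators, on exact intervals (the plan names no interval method for response), and on at least one case being misattributed, for which the documents give no rate.

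It would go too far to infer that the trial's main conclusions are at risk. Response is an exploratory objective, the analyses are descriptive, and no escalation or MTD decision uses it.

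**What to change.** - **Section 9.1.4:** report the response proportion by component, with imaging or marker (objective) response shown separately from clinical-only response. Flag clinical-only responders who had drainage or radiotherapy before the assessment.
- **CRF and Section 5.7:** record the date and volume of each paracentesis and any radiotherapy. Interpret girth or symptom change together with the change in drainage frequency, without excluding it outright.
- **Sections 5.7 and 9.1.4:** do not count shrinkage of a lesion irradiated on study towards response.
- **Section 5.3 and Appendix C:** measure girth before the infusion on the dosing days where it is scheduled, and add it to the C4D14 list.
- **Section 6.3.2:** reconcile the radiotherapy exception with the sentence on removing subjects who require a listed treatment. Which should stand is for the sponsor to decide.

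The cost is slightly more data entry, one tape measurement at an existing visit, and possibly a lower headline response rate.
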